## 7. Study Endpoints

	Screen -ing	First 24 hours Post partu m	1-7 days*	2 weeks	4 weeks	6 weeks	8 weeks	12 weeks	24 weeks END	Up to 1 year pp	Up to 5 years pp
Intake	X										
Postpartum contraception counseling satisfaction survey	X				X						
Device Insert		X			X	X					
Exclusive breastfeeding			X	X	X		X	X	X		
Breastfeeding discontinuation				X	X		X	X	X		
Retrospective Breastfeeding Discontinuation Chart Review Form										X	
Contraceptive use			X		X		X	X	X		X
Diary collection				X	X		X				
Mood (EPDS)				X	X		X				
Sexual function (FSFI)					X		X	X			
Bleeding log review				X	X		X				

7.1. The primary endpoint of this research are to compare continuation of lactation at eight week postpartum between women in the immediate with standard group.

The secondary endpoints of this research are to compare number of days of postpartum bleeding, postpartum sexual function as measured by FSFI score, and postpartum mood as measured by EPDS score, time to resumption of sexual activity, exclusive breastfeeding method, factors associated with discontinuing breastfeeding, timing of breastfeeding discontinuation, patient satisfaction with postpartum contraception counseling and the implant and patient satisfaction with bleeding pattern between the immediate and standard insertion groups.

As in other studies of breastfeeding and hormonal contraception, we will continue to follow women out to 6 months. A survival analysis will be performed to determine longer-term effect of hormonal contraception on breastfeeding.

**PROTOCOL TITLE:** Effect of immediate versus standard postpartum insertion of the contraceptive implant on breastfeeding outcomes

- 7.2. The primary study endpoint is also a safety endpoint: breastfeeding continuation through 8 weeks. We have developed a Data Safety and Monitoring Plan related to these endpoints (please see below).
- 7.3. No exploratory endpoints will be conducted in this research.

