A research staff will keep a record of contact information for all participants. The staff will schedule visits for standard insertions at 4 weeks postpartum, will contact care provider to let them know the patient is participating in the study and the date of the appointment for the implant insertion. We will schedule standard insertion at 4 weeks postpartum in order to have a 2 week period to reschedule the participant if necessary. UNM appointments can be made at the Center for Reproductive Health Clinic (CRH) for increased convenience and to improve follow up if a participant cannot return to her antepartum clinic.

Research staff will contact participants randomized to the standard insertion group one week before the appointment to remind her of her appointment and will contact the care provider by a message in the EMR to let them know they date of the appointment for the implant insertion. Research staff will coordinate any necessary appointment rescheduling. Research staff will track this information for the purpose of the study CONSORT flow diagram.

Utah's research coordinators will have access to UNM's REDCap and will randomize and enter baseline data. They will also enter the study participants contact information (phone number or email) which is how they will receive the follow up study questionnaires.

UNM will call UNM participants and Utah will call Utah's participants for the follow up for the contact periods at 2, 4, 8, 12, and 24 weeks postpartum will be made by each site's research team to their respective study participants by phone calls, text messages or email. The text message and the emails will include a link to REDCap to access the follow up questionnaire to be completed by the participant. When/if the patient is contacted through phone call the UNM and Utah research staff will only contact their respective participants for completion of the questionnaires in REDCap.

**PROTOCOL TITLE:** Effect of immediate versus standard postpartum insertion of the contraceptive implant on breastfeeding outcomes

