Retrospective Breastfeeding Survey	In-person, telephone and/or online via UNM's REDCap	2, 4, 8, 12, 24 weeks postpartum	Breastfeeding continuation, exclusivity, reasons for discontinuation if applicable, infant weight, resumption of intercourse, and satisfaction with contraception
Retrospective Breastfeeding Discontinuation Chart Review Form	Medical Chart Review	Up to 1 year pp	Breastfeeding continuation if no response from survey. Infant feeding data as clinically described in the infant chart up to 1 year* postpartum may be collected if no response to survey and no data is available in the patient's chart.
Retrospective Contraceptive Use Chart Review	Medical Chart Review	Up to years pp*  *Nexplanon can be used for up to 5 years after insertion	Nexplanon use at any of the timepoints (2, 4, 8, 12, 24 weeks postpartum). We will review the mother's chart up to 5 years postpartum if contraceptive use data is not obtained from surveys or available from chart review within the first year postpartum.

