## 13.Data Analysis

13.1 We will conduct a primary analysis per protocol and a secondary analysis per intention to treat. The rationale behind this strategy is to analyze both approaches and examine the result for consistency. A Repeated measures ANOVA analysis will be used for continuation of breastfeeding. To evaluate secondary outcomes between the two

**PROTOCOL TITLE:** Effect of immediate versus standard postpartum insertion of the contraceptive implant on breastfeeding outcomes

groups we will use the T-test, Wilcoxon Rank Sum test, Chi-squared test, or Fisher's exact test as appropriate. Secondary outcomes to be evaluated are to compare time of exclusivity of breastfeeding, mix breastfeeding, factors associated with discontinuing breasts feeding, time of breastfeeding discontinuation and patient satisfaction with postpartum contraception counseling and with timing of placing the implant between both groups. If there are significant differences between treatment groups, multivariable linear (for continuous outcomes) and logistic (for dichotomous outcomes) regression will be utilized in addition to control for confounding.

13.2 This study is a non-inferiority trial designed to demonstrate that immediate postpartum insertion of the ENG implant is non-inferior to standard ENG implant insertion with respect to the proportion of women who fail to breastfeed by 8 weeks after delivery. The failure rate for continuation of breastfeeding under the current treatment, standard insertion, is expected to be 30%.

The following sample size determination and plan for data analysis was developed in conjunction the University of New Mexico Clinical and Translational Science Center (CTSC). The non-inferiority margin for both primary outcomes is 15%, meaning that immediate insertion can be regarded as non-inferior (in terms of breastfeeding continuation) to standard insertion if the difference in rate with immediate insertion is no more than 15% worse than with standard insertion. To achieve 80% power with a 1-sided Type 1 error of 5% utilizing the Z test (unpooled) 62 participants are required in each group for a total 124. Accounting for the expected loss of follow up of 20%, the total subjects 149, round to 150. We intend to enroll up to 200 participants due to unanticipated loss to follow up, so this should ensure that we have enough data for data analysis.

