## **15. Withdrawal of Subjects**

- 15.1 The research team will provide thorough screening to see if the patient will meet inclusion and exclusion criteria. If any circumstances arise such participant experiencing exclusion criteria during study participation or fail to follow study procedures such as having the implant placed or removed before the study ends, the participant will be notified and withdrawn from the study without their consent.
- 15.2 Participants may have their implant removed at their request at any time. However, removal of the implant automatically terminates participation in the study and no data will be collected further. The data that was already collected from those participants that withdraws or was withdrawn from the study will be used for data analysis.
- 15.3 NA
- 15.4 Participants may withdraw from study involvement at any point in time and this will not affect their ability to obtain standard clinical care that day. All data points will be collected on the date of the procedure and therefore we anticipate loss to follow up and withdrawal rates will be low. Participants will be given the information on how to withdraw in the study consent.
- 15.5 The authorization for the use and disclosure of the participant health information for this study shall not expire unless the participant cancels this authorization. The health information will be used or disclosed as long as it is needed for this study. However, the participant may withdraw her authorization at any time providing a notification to the UNM investigators in writing to notifying the study team about the withdrawal. To do this, a letter should be sent to:

[name]  
Department of Obstetrics and Gynecology  
[name]  
[name]

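### Section 15 stops follow-up when the implant is removed and withdraws women whose implant is not placed, so the intention-to-treat check cannot cover all randomised women and no rule is given for the missing outcomes

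*Combined protocol and SAP*

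**What the plan says.** Section 3.1 sets the primary endpoint as any breastfeeding at eight weeks. Section 13.1 says "We will conduct a primary analysis per protocol and a secondary analysis per intention to treat" and gives consistency between the two as the reason. It defines neither set and has no rule for a woman whose week-8 status is unknown.

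Section 15 ties follow-up to what happens after randomisation:

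- **15.1:** if a woman meets an exclusion criterion during the study, or should she "fail to follow study procedures such as having the implant placed or removed before the study ends, the participant will be notified and withdrawn". The exclusion list in 4.2 includes drugs that inhibit lactation.
- **15.2:** "removal of the implant automatically terminates participation in the study and no data will be collected further". It adds: "The data that was already collected from those participants that withdraws or was withdrawn from the study will be used for data analysis".
- **15.4:** loss and withdrawal are expected to be low because "All data points will be collected on the date of the procedure".

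Three other places bear on this. Section 12 (follow-up procedures) says of the standard arm: "We will schedule standard insertion at 4 weeks postpartum in order to have a 2 week period to reschedule the participant if necessary". The instrument table in Section 12 gives the chart-review form this purpose: "Breastfeeding continuation if no response from survey". Section 7.1 adds, for the follow-up to six months: "A survival analysis will be performed to determine longer-term effect of hormonal contraception on breastfeeding".

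**The concern.** Removal can happen at any time from the first day in the immediate arm. Non-placement in the standard arm is established between about weeks 4 and 6. Both fall before week 8. Because data already collected are kept, women who stopped and reported it before withdrawal count as failures. Women still breastfeeding at withdrawal have no week-8 value. The outcome is therefore missing according to implant status and breastfeeding status, both of which arise after randomisation, and the main trigger differs by arm.

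The intention-to-treat analysis is the safeguard against a per-protocol result shaped by such selection. If the same women are missing from it, or enter by an undocumented choice, agreement between the two analyses shows little. Removals after week 8 leave the primary endpoint intact but shorten follow-up for the six-month survival analysis.

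**Working it through.** **Inputs from the plan.** Margin 15 points, one-sided 5%, unpooled Z test, 30% discontinuation under standard insertion, 62 analysed per arm, 20% loss (13.2); 75 per arm (3.1); up to 200 enrolled (5.3). The plan gives no removal or non-placement rate.

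**The plan's own figures.** 124 × 1.2 = 148.8, which reproduces 149. The 62 per arm does not follow from the stated inputs if both arms have 30% discontinuation: 2 × 0.21 × (1.645 + 0.842)² / 0.15² = 115.4, or 116 per arm. That is a separate point. It matters here only because it makes the slack below thinner.

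**1. Can the missing outcomes be recovered?**

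| Situation before week 8 | Week-8 outcome under the plan |
|---|---|
| Stopped and recorded, then withdrawn | Known failure (15.2) |
| Still breastfeeding, implant removed | Unknown; 15.2 bars further collection, chart review included |
| Still breastfeeding, implant never placed | Withdrawn (15.1); end of collection implied, not stated; chart review neither barred nor extended to her |

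**2. How many women change the conclusion?** Let pI and pS be the proportions stopped in the immediate and standard arms. Upper limit = pI − pS + 1.645 × √[pI(1−pI)/n + pS(1−pS)/n].

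| n per arm | Stops, immediate vs standard | Upper limit (points) | Within 15? |
|---|---|---|---|
| 75 | 22 vs 22 | 0 + 1.645 × 7.435 = 12.23 | yes |
| 75 | 23 vs 22 | 13.64 | yes |
| 75 | 24 vs 22 | 2.67 + 1.645 × 7.527 = 15.05 | no |
| 75 | 22 vs 19 | 4.00 + 1.645 × 7.270 = 15.96 | no |
| 62 | 19 vs 19 | 13.62 | yes |
| 62 | 20 vs 19 | 15.33 | no |
| 100 | 30 vs 30 | 10.66 | yes |
| 100 | 34 vs 30 | 14.84 | yes |
| 100 | 35 vs 30 | 15.88 | no |

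Starting from equal counts, the conclusion reverses if 2 immediate-arm women of 75 were counted as continuing but had stopped (1 of 62, 5 of 100). In the standard arm of 75 it reverses if 3 women were counted as stopped but had continued.

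**3. Bounds.** The margin equals 0.15 × 75 = 11.25 women. Twelve unknown women in one arm of 75 span 12/75 = 16 points. If 8 women in each arm are unknown (about 10%, an assumption), the difference is undetermined by ±8/75 = ±10.7 points.

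**4. Direction, if unknown women are simply dropped.** Let p be the true stopping rate, m the share of the arm withdrawn, r the share of withdrawn women who stop by week 8, and s the share of those stops recorded before withdrawal. Then

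observed rate = [p − m·r·(1−s)] / [1 − m + m·r·s].

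Chance of concluding non-inferiority = Φ{[0.15 − (pI − pS)]/SE − 1.645}, with 62 per arm. With no selection and 30% in both arms, SE = √(0.42/62) = 0.0823, giving Φ(0.178) = 57%. The values of m, r and s are assumptions.

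*(a) No true effect; standard-arm women not placed; r = 0.5:*

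| m | s | Observed standard rate | Chance of non-inferiority |
|---|---|---|---|
| 5% | 0 | 28.9% | 52% |
| 5% | 0.5 | 29.9% | 56% |
| 5% | 1 | 30.8% | 60% |
| 20% | 0 | 25.0% | 35% |
| 20% | 0.5 | 29.4% | 54% |
| 20% | 1 | 33.3% | 71% |

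*(b) True 15-point deficit (45% vs 30%), where the nominal error is 5%; immediate-arm women with removal:*

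| m | r | s | False non-inferiority |
|---|---|---|---|
| 2% | 1 | 0 | 6.5% |
| 10% | 1 | 0 | 17.7% |
| 10% | 1 | 0.5 | 9.6% |
| 2% or 10% | 1 | 1 | 5.0% |
| 10% | 0.45 | 0 | 5.0% |
| 10% | 0.45 | 1 | 2.6% |

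Selection can push the result either way, depending on quantities that the plan does not collect once women are withdrawn.

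**The case against.** The strongest reply has four parts.

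- **The primary analysis is per protocol.** On any ordinary reading it leaves these women out whether or not week 8 is recorded. That is right: the point concerns the intention-to-treat check, and the limits above are not forecasts of the trial's verdict. But that check is the plan's only stated safeguard.
- **The bar on further data is explicit only for removal.** For non-placement it is inferred from a loosely worded sentence, and Section 12 has a retrospective survey and chart review that might recover some outcomes. This stands as a limit on certainty. Those tools are written for missed contacts and survey non-response, and nothing extends them to withdrawn women.
- **The extreme scenarios are unlikely.** A missed insertion is normally established around week 6, after the 2- and 4-week surveys, so s near 0 in the standard arm is a corner case. With s at two-thirds or more, table (a) shifts towards non-inferiority only (about 58–60% at 5% not placed, 60–71% at 20%). The 17.7% needs every removed woman to stop and none to be recorded first; with 10% removed, r = 0.6 and s = 0.5 the figure is 4.8%. These are fair readings, and the extremes should be taken as bounds.
- **The tipping counts assign unknown women in the way that favours non-inferiority in each arm.** Dropping two immediate-arm women instead (22/73 vs 22/75) gives 13.2 points. The two-woman tip also crosses the margin by only 0.05 point, and 62 is the number left after loss. All true, but it shows that the answer turns on a choice the plan does not make.

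Reminders and the two-week rescheduling period reduce non-placement but do not deal with it when it happens.

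**Conclusion.** The concern holds and should be fixed. Sections 15.1–15.2 make outcome collection depend on implant status after randomisation, and 13.1 has no rule for the resulting gaps. For removal this is explicit; for non-placement it is the natural reading of an unclear sentence. The size of the bias cannot be stated because the documents give no withdrawal rates. What can be stated is sensitivity: from equal observed rates, reclassifying 2 women in an immediate arm of 75 (1 of 62, 5 of 100) moves the upper limit past 15 points. Part of that thin slack comes from the sample size. No direction of bias is claimed. The reason 15.4 gives for expecting few withdrawals conflicts with the 2- to 24-week surveys and the 20% loss allowance, so those passages need reconciling.

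**What to change.** 1. In 15.1 and 15.2, separate not receiving or no longer having the implant from leaving the study. With the woman's agreement, continue the existing 2- to 24-week surveys and chart review unless she withdraws consent, and say so for both non-placement and removal.
2. In 13.1, define the intention-to-treat set as all randomised women in their assigned arm whatever their implant status, and define the per-protocol set in advance.
3. State one rule for unknown week-8 status. Add a tipping-point analysis that varies the unknown women in each arm separately, from all continued to all stopped.
4. Report the number withdrawn in each arm by reason, with breastfeeding status at withdrawal.
5. Reconcile 15.4 with the follow-up schedule and the loss allowance.

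The cost is protocol and consent wording, plus a few more surveys or chart reviews with instruments already in place. Women already withdrawn would have to agree to further contact. A woman's freedom to have the implant removed is unchanged.

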## **16. Data Management/Confidentiality**

- 16.1. Only IRB-approved study team members will have access to study data and participant materials.
- 16.2. A study identification number will be assigned to each participant in lieu of using their personal information for identification (e.g., name). All participant data will be de-identified. Participant data will be stored separately from any identifiers to protect patient privacy. We will use de-identified cover sheets for document packets containing PHI.
- 16.3. This study will not be collecting information considered extremely sensitive or require additional protections such as HIV, genetic test results, mental health information, substance abuse information, and/or criminal records.
- 16.4. Data will be entered into the data collection software, REDCap, by research staff. Research staff will have completed institutional training prior to initiation of the study. Additionally, only study staff will have access to the REDCap records.
- 16.5. Study packets will be stored in a secure file cabinet located in the research office. These cabinets will be kept locked at all times. In a separately locked file cabinet, stored in the same room, the study consents will be stored. This second file cabinet is locked with a second, separate key from all other study materials.
- 16.6. The list that links participant information to the study identification number will be destroyed after data analysis is complete. Data will be stored for five years, and then will be destroyed. Study records of minors will be retained until the minor turns 22 years old, and then will be destroyed.

## **17. Data and Specimen Banking**

NA, no data or specimens will be banked or archived locally for future use.

## **18. Risks to Subjects**

- 18.1. The ENG implant has been associated with mild side effects including unpredictable bleeding patterns, mood swings, weight gain, acne, depressive mood, vaginitis, breast pain, viral infections, stomach pain, painful periods, nervousness, back pain, headache, dizziness, or nausea and vomiting. In addition, the potential insertion procedure side effects and complications include pain, irritation, swelling, bruising, scaring, infection, nerve injury, implant break and then need for an extensive procedure for removal. Everyone taking part in the study will be followed carefully for any side effects. There are risks of stress, emotional distress, inconvenience and possible loss of privacy and confidentiality associated with participating in a research study. There is also the possible risk of decreased breast milk production. Current but limited data suggest there is no decreased breast milk with progestin-only methods.

The UNM Hospital and its affiliated clinics are staffed by providers trained in postpartum contraception.

**PROTOCOL TITLE: Effect of immediate versus standard postpartum insertion of the contraceptive implant on breastfeeding outcomes**

The implant has side effects – because of the small amount of hormone, it is unlikely and has not been shown in studies to increase the risk of depression. (29)

Postpartum implant insertion will be inserted according to the standardized procedure approved by the FDA and only by providers certified to insert the implant by Merck.

Regarding data collected for assessment of postpartum mood:

EPDS results will be scored weekly as they are obtained. The research coordinator will forward scores to the on-call study co-investigator as soon as possible/on the day they are obtained. For scores <10 (with a score of 0 for question 10) no immediate action is needed, and the study participant will be reevaluated at the next study interval. For scores < or = to 10 (with a score of 0 for question 10), the co-investigator will 1) call the study participant as soon as possible/on the day they are obtained and offer referral to counseling and/or for suicidal ideation, to the crisis hotline number (National Suicide Prevention [contact]). For women without suicidal ideation or acute crisis, the study co-investigator will offer an appointment in the OB-GYN perinatal mood disorders clinic, Journeys with a counselor within the next 5 days. Study participants with a non-zero score for question 10 will be contacted by the study co-investigator as soon as possible/on the day they are obtained by telephone and suicide risk will be assessed using the SAHMSA SAFE-T 5-step method (23). For moderate and high-risk study participants, immediate referral to UNM Psychiatric Urgent Care Clinic or Psychiatric Emergency Services will be made in addition to provision of the crisis hotline number above. All study co-investigators are competent to manage patient responses on the Edinburgh.

- 18.2. NA, no procedures may have risks to the subjects that are currently unforeseeable.
- 18.3. NA, no procedures may have risks to an embryo or fetus should the subject be or become pregnant. The implant is a contraceptive method.
- 18.4. NA, there is no risks to others who are not subjects.
- 18.5. To minimize the probability or magnitude of risks of this study the insertion will be performed as per FDA guidelines. However, side effects cannot be prevented.

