- Once the woman is enrolled in the study a line will be added to the Antenatal Supplemental Visit Form stipulating the patient's participation in the study and the coordinator's phone number: Ex: "[name] study patient – page at admission ####-#####\*\*." This Form is a section of the EMR that is updated at each visit by the clinic provider with important/current antenatal issues; it is standard that the contraceptive plan for each patient is recorded here.

*Identification of study patients on L&D*

- The PCP on L&D may identify study patients who self-identify as being in the study. They will also be alerted by the "Study Patient" in the antepartum record if the patient has been enrolled antepartum. They will notify the research coordinator who will carry a phone during working hours.
- A reproductive health on-call fellow/attending will be designated 24-7 to ensure randomization and implant insertion within 24 hours for those randomized to the immediate group. After hours (nights and weekends), the research cell will forward to the reproductive health on-call fellow or attending. In addition, the voice message for the research cell will direct callers to contact the reproductive health on-call fellow through Amion, the hospital online paging system. A calendar will specify which co-investigator is on call for study patients.
- The PCP on L&D will call the research coordinator/call physician by phone or by text message that a study patient arrived on L&D for her birth.
- The research coordinator will review the list of admitted patients to L&D twice a day (8 AM and 4 PM) and once daily on Mother Baby Unit and Ob-Special care (Ob-Gyn wards) to identify enrolled study patients. This modality has been used with other studies in the department of Ob-Gyn and has been successful.

*Randomization*

- University of Utah coordinators will have access to UNM's REDCap to obtain randomization and enter any data collected for their participants.
- The research coordinator will access REDCap to obtain the randomization assignment for study patients (enrolled antepartum or on L&D not in labor) shortly after admission to L&D for a birth. The reproductive health physician on call will be notified

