The questionnaires will contain data about breastfeeding, postpartum depression, and sexual function. A paper diary will be provided to aid the participant in daily recording of data. We will also include a retrospective data collection instrument to account for those we miss at the primary data collection points for breastfeeding information. If the primary questions have been answered either prospectively or retrospectively, then they get the normal prospective survey. If participants do not meet this criteria or if they miss a previous survey, then they will receive a retrospective survey. The diary will be collected at 2, 4, and 8 weeks. If possible, 2-3 good phone numbers will be obtained as well as addresses for each participant. Participants will have a phone number to contact study personnel at their specified site during standard work hours: Monday-Friday 8am- 4:30 pm with any concerns or adverse events. If they call after-hours, a voicemail system will be available, and the participant will be contacted the next working day.

*Data collection instruments*

Data collection instrument	Manner of collection	Timing	Included data
Enrollment form	Medical chart review  In-person, telephone and/or online via UNM's REDCap	After delivery  At enrollment	Participant & neonate medical history, delivery details  contraceptive history, contraceptive bridge-methods, lactation history, lactation and work expectations
Contraceptive Counseling Survey	In-person, telephone and/or online via UNM's REDCap	At enrollment and 4 weeks postpartum	Satisfaction with contraceptive counseling
Breastfeeding Survey	In-person, telephone and/or online via UNM's REDCap	2, 4, 8, 12, 24 weeks postpartum	Breastfeeding continuation, exclusivity, reasons for discontinuation if applicable, infant weight, resumption of intercourse, and satisfaction with contraception
EPDS	In-person, telephone and/or online via UNM's REDCap	2, 4, 8 weeks postpartum	Postpartum depression scale
FSFI	In-person, telephone and/or online via UNM's REDCap	4, 8, 12 weeks postpartum	Sexual function scale

PROTOCOL TITLE: Effect of immediate versus standard postpartum insertion of the contraceptive implant on breastfeeding outcomes

Bleeding diary	Paper or UNM's REDCap	Reviewed at 2, 4, 8 weeks. Collected at 2, 4, and 8 weeks	Bleeding patterns Side effects

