## 1. Data Transfer/Sharing (Checklist)

*Complete this checklist if the research involves transferring/sharing of data with an external entity (institution, company, etc.).*

A. Will data be transferred/shared with an external entity (institution, company, etc.)?

Yes

No. **The remainder of this section does not apply.**

B. Indicate if the data is incoming and/or outgoing: incoming

C. Provide the name of the entity that data will be transferred/shared with: University of Utah

D. Provide the contact name, email and phone number with whom data is being transferred/shared with: [name], [contact]

E. Who is responsible for transmission of the data? *Utah's approved study team members*

F. Who is responsible for receiving the data? UNM's approved study team members

G. Describe how the data will be transferred/shared. Please note data cannot be transferred/shared without assistance from UNM HSC IT. **Requesting HSC Central IT Transfer is detailed on the Sponsored Projects website:** Through UNM's REDCap, *Utah's study team members will be set up as a UNM affiliate to gain access to UNM's REDCap database to enter the Utah's study participant's email or phone number, the REDCap electronic survey will then be sent directly to the study participant for them to complete the electronic survey and the data will automatically load into UNM's REDCap database. An approved Utah study team member that is a UNM affiliate with a login to UNM's REDCap could also enter the survey data in the case of the data being collected in person or over the phone.*

H. For data being transferred/shared with outside locations or entities, describe the following: NA

- Where is data storage and how will it be maintained in a secure manner (i.e. encryption, password protection, use of Qualtrics or REDCap, etc)?
- What is method in which data will be collected and stored (i.e. electronic, hard copy, etc)?
- How long will the data be stored?
- Who will have access to data?

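### In Section 18.1 the word 'weekly' for EPDS scoring conflicts with the same-day duties around it, and no alert or review of online forms is described

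*Combined protocol and SAP*

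**What the plan says.** In Section 18.1, the part on postpartum mood data opens with "EPDS results will be scored weekly as they are obtained". The next sentence reads "The research coordinator will forward scores to the on-call study co-investigator as soon as possible/on the day they are obtained". For totals in the band that calls for action, the co-investigator is to "call the study participant as soon as possible/on the day they are obtained and offer referral to counseling". Women with a non-zero answer to question 10 "will be contacted by the study co-investigator as soon as possible/on the day they are obtained", by telephone, and their suicide risk is then assessed.

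Section 12 describes how the form arrives. Its table of instruments lists the EPDS at 2, 4 and 8 weeks, taken in person, by telephone or online. Under Follow-up procedures it says "The questionnaires will contain data about breastfeeding, postpartum depression, and sexual function" and "The text message and the emails will include a link to REDCap to access the follow up questionnaire to be completed by the participant". Item G of the Data Transfer/Sharing checklist says that the survey goes straight to Utah participants "for them to complete the electronic survey and the data will automatically load into" the UNM REDCap database.

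**The concern.** The first sentence of the procedure holds two timings: a weekly frequency and an on-receipt trigger. Every protective step that follows depends on someone having looked at the form. If a site took 'weekly' as its scoring schedule, the same-day duties could be met in form while an answer to question 10 stayed unread for days.

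This matters most for forms completed through the link. In person or by telephone, a staff member hears or sees the answers. Online, nobody need be present. The trial itself puts this question to women at 2, 4 and 8 weeks postpartum, and 18.1 treats a non-zero answer as urgent. Staff at two sites work from the same text, and each site contacts its own participants, so wording that two teams can read differently is worth settling.

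**Working it through.** The plan gives no figure to reproduce here. The check is mainly a comparison of texts, with a short count to show scale.

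**1. Timing words in 18.1, side by side.**

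| Step | Timing written |
|---|---|
| Scoring | weekly, and also as results come in |
| Forwarding the score | as soon as possible or same day |
| Call for a total that requires action | as soon as possible or same day |
| Call for a non-zero question 10 | as soon as possible or same day |

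Three of the four steps are same-day only. The scoring step carries both timings.

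**2. When the same-day clock starts.** In the scoring sentence, what is obtained is the EPDS result, which most naturally means the completed form. On that reading all four steps agree. In the forwarding sentence, what is obtained can be the score. On that reading a weekly scoring session followed by same-day forwarding also fits the words. The first reading is the better one, but 'weekly' keeps the second available.

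**3. What brings an online form to staff attention.** Checklist item G describes automatic loading for Utah participants. Section 12 sends the same kind of REDCap link to participants at both sites, so I take the same to hold at UNM. Section 16.4 says research staff enter data, which fits in-person and telephone forms but not self-completed ones. Looking for a prompt or review elsewhere:

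- The round-the-clock on-call cover in Section 12 is there to secure randomization and insertion within 24 hours.
- The participant telephone line runs Monday to Friday, 8 am to 4:30 pm, with call-back the next working day. It handles calls from women, not submitted forms.
- Section 14 monitoring is at least quarterly, and its list of reviewed data does not name the EPDS.

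None of these describes an alert or a review of submitted EPDS forms.

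**4. Possible wait.** Scored on receipt: same day. Batched weekly: at most 7 days, and on average 7 / 2 = 3.5 days if forms arrive evenly through the week (an assumption).

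**5. Number of forms under the rule.** Inputs are 3 time points (Section 12), 150 participants (3.1), up to 200 (5.3), and 20% expected loss (5.3).

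- Scheduled: 3 × 150 = 450; 3 × 200 = 600.
- After 20% loss, applied equally at each time point (an assumption): 0.8 × 450 = 360; 0.8 × 600 = 480.
- For each 1% of forms with a non-zero question 10: 0.01 × 360 = 3.6 up to 0.01 × 600 = 6.0 forms.
- Multiply by the online share, which is not given (0 to 1). The exposed number per 1% is therefore anywhere from 0 to 6.0.

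The 1% is a unit, not an estimate. These counts give scale and show no actual effect.

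**The case against.** The strongest reply is that the weekly-batch reading is weak. It makes the second half of the scoring sentence pointless and empties three later instructions of their purpose. 'Weekly' may be loose drafting for forms that come in week by week from a rolling cohort. Question 10 is a single item, so a non-zero answer can be acted on without a total. A coordinator who left one unread for a week would be acting against the plain aim of the paragraph. This stands as far as intent goes: same-day handling is what the plan means.

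A second reply is that alerts and work-lists usually sit in the database build or a manual, and that 18.1 already assigns the duty, the recipient and the action. This stands in part. Silence in the protocol does not show that no alert exists. However, the protocol is not merely silent: it writes a weekly frequency into a safety procedure. The contrast with the twice-daily checks of labor and delivery lists in Section 12 adds little, because those serve the 24-hour insertion deadline.

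A reader might go further and infer that the trial plans to leave forms for a week, that 'weekly' is the only timing given, or that hundreds of forms are at risk. The documents support none of these. Same-day wording appears three times, no batch is described, and the exposed number depends on two unknown shares and could be zero.

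**Conclusion.** The point holds as a conflict of wording in an operative safety procedure. 'Weekly' contradicts the same-day instruction that dominates 18.1. Taken literally, it would allow a form completed online with a non-zero question 10 to wait up to 7 days, since no staff step, alert or review is described between submission and scoring. The 7 days is the outer limit of the word, not a planned or observed delay. In-person and telephone forms are not exposed in this way.

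The conclusion rests on the protocol text alone. It assumes that UNM link forms load as Utah forms do, and it would shrink to a one-sentence clarification if an alert is already built. It is a cheap improvement, for participant safety only. The primary endpoint, power and analysis are unaffected.

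**What to change.** Replace the scoring sentence in 18.1 with one stating that EPDS results will be scored on the day the form is submitted. This removes 'weekly' and starts the same-day clock at submission.

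Set REDCap to send an automatic alert to the on-call co-investigator already designated in 18.1, with a Utah recipient for Utah participants, for any non-zero question 10 or a total at the action threshold. The question 10 trigger needs no cut-off. The threshold for the total is for the investigators to state. If such an alert already exists, say so in 18.1.

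The cost is one line of wording, a small REDCap set-up and test, and occasional out-of-hours alerts. The on-call calendar in Section 12 is written for labor and delivery, so the team should confirm that it also covers EPDS alerts. If no alert can be set, a named person checking submitted forms every day, weekends included, would serve, but that could need extra staff, so the alert is preferable.
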